## **12. CONFIDENTIALITY/PUBLICATION OF THE STUDY**

The existence of this Study is confidential and should not be discussed with persons outside of the Study. Results will be submitted for publication and presentation at national and/or international meetings. A manuscript will be submitted to peer-review journals for publication but there is no guarantee of acceptance.

All study data will be collected on appropriate Case Report Forms (CRFs). No protected health information will be included on the forms. CRFs will be retained in the patient's file for a minimum period of 3 years. Collected information will only be used for purposes of this study and no information will be sold to third parties. The following people will have access to your study records:

- Study Doctor and staff involved with the study
- Study Monitor or Auditor
- Sponsor Company or Research Institution
- Review boards or accrediting agencies
- Other State or Federal Regulatory Agencies

The de-identified data may be shared with other researchers for future analysis.

## **13. QUALITY COMPLAINTS AND ADVERSE EVENTS**

All subjects will be monitored for adverse events over the course of the study. A place to record any adverse event is included on each case report form.

### ***13.1. General Information***

An Adverse Event (AE) is any untoward medical occurrence in a subject who is administered a study treatment regardless of whether or not the event has a causal relationship with the treatment. An AE, therefore, can be any unfavorable or unintended sign (including an abnormal laboratory finding), symptom, or disease temporally

associated with the study treatment, whether or not related to the treatment. In clinical studies, an AE can include an untoward medical occurrence occurring at any time, including run-in or washout periods, even if no study treatment has been administered.

### ***13.2. Monitoring for Adverse Events***

At each visit, after the subject has had the opportunity to spontaneously mention any problems, the Investigator should inquire about AEs by asking if the patient has any problems.

### ***13.3. Procedures for Recording and Reporting AEs and SAEs***

Subsequent to signing an informed consent form, all untoward medical occurrences that occur during the course of the study must be documented on an Adverse Event Form (AEF). A separate AEF must be filled out for each event. When possible, signs and symptoms indicating a common underlying pathology should be documented as one comprehensive event. For each recorded event, the AE documentation must include the onset date, outcome, resolution date (if event is resolved), intensity (i.e., severity), any action with study treatment taken as a result of the event, and an assessment of the adverse event's relationship to the study treatment.

#### **Nonserious Adverse Events**

A nonserious AE is defined as any untoward change in a subject's medical health that does not meet serious criteria noted below (e.g., is not life-threatening, does not require hospitalization, does not prolong a current hospitalization, is not disabling, etc.). All adverse events must be reported regardless of whether or not they are related to the study treatment.

For nonserious adverse events, an AEF containing all available information will be collected on a routine basis and submitted to the Medical Monitor at the close of the study.

#### **Serious Adverse Events**

A serious adverse event (SAE) is defined as any adverse experience that meets any of the following criteria:

- Results in death.
- Is life-threatening.

NOTE: Life-threatening means that the subject was at immediate risk of death from the reaction as it occurred; i.e., it does not include a reaction which hypothetically might have caused death had it occurred in a more severe form.

- Requires inpatient hospitalization or prolongation of existing hospitalization.  
NOTE: In general, hospitalization signifies that the individual remained at the hospital or emergency ward for observation and/or treatment (usually involving an overnight stay) that would not have been appropriate in the physician's office or an out-patient setting. Complications that occur during hospitalization are AEs. If a complication prolongs hospitalization or fulfills any other serious criteria, the event is serious. When in doubt as to whether "hospitalization" occurred, the event should be considered serious.

- Results in persistent or significant disability/incapacity. Disability is defined as a substantial disruption of a person's ability to conduct normal life functions.  
NOTE: The term disability means a substantial disruption of a person's ability to conduct normal life functions. This definition is not intended to include experiences of relatively minor medical significance such as uncomplicated headache, nausea, vomiting, diarrhea, influenza, or accidental trauma (e.g., sprained ankle) which may interfere or prevent everyday life functions but do not constitute a substantial disruption.
- Is an important medical event. An important medical event is an event that may not result in death, be life-threatening, or require hospitalization but may be considered an SAE when, based upon appropriate medical judgment, it may jeopardize the subject and may require medical or surgical intervention to prevent one of the outcomes listed in the definitions for SAEs. Examples of such medical events include allergic bronchospasm requiring intensive treatment in an emergency room or at home, blood dyscrasias or convulsions that do not result in subject hospitalization, or the development of drug dependency or drug abuse.  
All available information on a serious adverse event(s) and any other associated AE, if applicable, must be forwarded to the study coordinator for forwarding to the Medical Monitor immediately (i.e., within one working day of the Investigator's or site's knowledge of the event) as follows:
  - In studies utilizing EDC (electronic data capture), all available information for the SAE and any associated AE(s) must be entered immediately into the EDC system.
  - Additional information for any applicable event is to be reported as soon as it becomes available.

In addition to the reporting of serious adverse events to the study Medical Monitor, the SAE must be reported to the IRB / IEC according to their requirements.

The investigator must document all adverse device events (serious and nonserious but related) and all serious adverse events (related and unrelated) on the Adverse Device Effect and Serious Adverse Event Form. Any device quality complaints will also be documented.

- **Both the Quality Complaint Form and the Adverse Device Effect and Serious Adverse Event Form must be e-mailed immediately to the study coordinator ([name]).**
- **Additional relevant information is to be reported as soon as it becomes available.**

#### 12.3.1 Intensity and Causality Assessments

For every adverse event and quality complaint, the investigator must assess the causality as Related or Not Related to the medical device under investigation. An assessment of causality will also be performed by the Medical Monitor utilizing the same definitions, as shown below:

#### ***Causality***

- Related** An adverse event or quality complaint classified as related may be either definitely related or possibly related where a direct cause and effect relationship with the medical device has not been demonstrated, but there is a reasonable possibility that the adverse event or quality complaint was caused by the medical device.
- Not Related** An adverse event or quality complaint classified as not related may either be definitely unrelated or simply unlikely to be related (i.e., there are other more likely causes for the adverse event or quality complaint).

Where appropriate, the investigator must assess the intensity (severity) of the adverse event as mild, moderate, or severe based on medical judgment with consideration of any subjective symptom(s), as defined below:

#### ***Intensity (Severity)***

- Mild** An adverse event is mild if the subject is aware of but can easily tolerate the sign or symptom.
- Moderate** An adverse event is moderate if the sign or symptom results in discomfort significant enough to cause interference with the subject's usual activities.
- Severe** An adverse event is severe if the sign or symptom is incapacitating and results in the subject's inability to work or engage in their usual activities.

The investigator must document any action taken (i.e., medication, intervention, or treatment plan) and outcome of the adverse event or quality complaint when applicable.

#### ***13.4. Follow-Up of Adverse Events and Quality Complaints***

The investigator is responsible for adequate and safe medical care of subjects during the study and for ensuring that appropriate medical care and relevant follow-up procedures are maintained after the study. Any additional data from these follow-up procedures must be documented and available to the study coordinator who, with the Medical Monitor, will determine when the data need to be documented on the CRFs.

#### ***13.5. Safety Analyses***

The type, severity, duration and frequency of reported ocular adverse events will be tabulated. Adverse events will also be summarized for events that were considered treatment-related.

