### **10. ANALYSIS PLAN**

#### ***10.1. Analysis Data Sets***

All subjects who are enrolled in the study will be evaluated for safety. Efficacy analyses will be performed based on data from those eyes where uncomplicated cataract surgery with Clareon IOL implantation was completed.

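### The planned safety outputs cover ocular events and treatment-related events only, so a non-ocular event judged Not Related, even a serious one, appears in no planned safety summary

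*Combined protocol and SAP*

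**What the plan says.** Section 13.5 (Safety Analyses) is the whole of the planned safety analysis and consists of two sentences. The first: "The type, severity, duration and frequency of reported ocular adverse events will be tabulated". The second: "Adverse events will also be summarized for events that were considered treatment-related".

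The collection and reporting rules in Section 13.3 are wider:

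- After consent, "all untoward medical occurrences that occur during the course of the study must be documented on an Adverse Event Form (AEF".
- Under Nonserious Adverse Events: "All adverse events must be reported regardless of whether or not they are related to the study treatment".
- Under Serious Adverse Events, the investigator must document "all serious adverse events (related and unrelated) on the Adverse Device Effect and Serious Adverse Event Form". These events go to the Medical Monitor within one working day, and "the SAE must be reported to the IRB / IEC according to their requirements".

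On causality, the subsection numbered 12.3.1 (which sits within Section 13) says that "the investigator must assess the causality as Related or Not Related to the medical device under investigation". The Medical Monitor also assesses causality, using the same definitions.

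On the safety population, Section 10.1 says: "All subjects who are enrolled in the study will be evaluated for safety".

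**The concern.** The plan collects all adverse events but specifies outputs for only some of them. An event reaches a planned summary if it is ocular or if it is judged treatment-related. An event that is neither has no place in the planned results, however serious it is.

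What is at stake is the completeness of the safety result. Section 12 plans publication, and a reader of the published report would expect to see all serious events and any deaths, whatever the attributed cause. Section 3 gives an enrolment age of 50 or older. Most of the seriousness criteria in Section 13.3 (death, threat to life, hospitalisation, disability) describe outcomes that need not be ocular. For non-ocular events, inclusion depends on a causality judgement, and with no control arm there is no between-group comparison against which to check such judgements.

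**Working it through.** No figure in the plan bears on this point, so the check sets the text on what is recorded against the text on what is summarised.

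**Step 1: what is recorded.** Section 13.3 covers all adverse events after consent, related or not, ocular or not. Serious events, related or not, also go on a dedicated form.

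**Step 2: what is summarised.** Sort events by organ and relatedness, and compare each class with the two outputs in Section 13.5.

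| Class of event | Ocular tabulation | Treatment-related summary | In a planned output? |
|---|---|---|---|
| Ocular, related | Yes | Yes | Yes |
| Ocular, not related | Yes | No | Yes |
| Non-ocular, related | No | Yes, if this summary is not itself confined to ocular events | Yes, on that reading |
| Non-ocular, not related | No | No | **No** |

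**Step 3: does seriousness bring an event back in?** Not on the text. The listed attributes are type, severity, duration and frequency. Severity is graded mild, moderate or severe under Intensity (Severity). Seriousness is defined separately, under Serious Adverse Events, by outcome criteria. Neither sentence of Section 13.5 uses seriousness to select or describe events.

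**Step 4: does another section fill the gap?** The only candidate is Section 10.2, which promises summaries at all measurement time points. It describes continuous and categorical variables, presents them for eyes completing the study, and does not mention adverse events. A subject who leaves early because of an adverse event (a reason listed in Section 9.5) would not be a completer. Section 10.2 does not fill the gap.

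**Step 5: which events could fall in the uncovered class?** Two examples follow from the definitions. Causality is judged against the device, so a systemic event attributed to surgery or anaesthesia rather than to the lens could be classed Not Related. And Section 13.1 counts events even where no study treatment has been given, so a non-ocular event between consent and surgery could be recorded and not summarised.

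**The case against.** The case for the planned scope is reasonable. The objective is refractive stability, no safety variable is listed among the primary, secondary or exploratory outcomes, and the study is small, short and single-arm. For an intraocular lens, the ocular events are the most informative class, and Section 13.5 tabulates all of them whatever their cause. The definition of Related is broad and takes in events that are only possibly related. Collecting more than one tabulates is not in itself a contradiction.

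Most of this stands, and it rules out several stronger readings that a reader might infer:

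- *That such events disappear.* They do not. They are documented, and serious ones are sent promptly to the Medical Monitor and reported to the IRB/IEC. They are absent from the planned summaries, not from oversight.
- *That the whole safety result turns on one investigator's unchecked causality call.* Ocular events are tabulated regardless of causality, and the Medical Monitor makes a second assessment. Causality decides inclusion only for non-ocular events.
- *That Section 13.5 contradicts the safety population.* Section 10.1 says which subjects are evaluated, not which events are tabulated. An ocular table covering all enrolled subjects is consistent with it.
- *That the report would show a false zero, to which an event rate or confidence bound could be attached.* The plan has no row for non-ocular unrelated events, so they would be unreported rather than reported as none.

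What the objection does not answer is the treatment of serious events. Case reporting is not a study result, and a focus on ocular findings gives no reason to leave a death or hospitalisation out of the summary. One might argue that type was meant to include seriousness. The term is undefined, so that cannot be excluded, but even then it would describe only the ocular events in that table.

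**Conclusion.** The point holds in a limited form. Section 13.5 leaves one class, non-ocular events judged Not Related, out of every planned safety summary, and this includes serious events and deaths. The consequence is an incomplete safety result. It has no bearing on the refractive endpoint, and there is no meaningful number to put on it.

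The conclusion rests on three assumptions. First, the treatment-related summary is taken to include non-ocular events; if it does not, the gap is wider. Second, treatment-related in Section 13.5 is taken to follow the device-based scale in the subsection numbered 12.3.1. Section 13.3 also speaks of relationship to the study treatment; if that were read to include the surgery, fewer events would be left out, but the class would remain. Third, the statement that no other output is planned rests on the available text. A part of Section 13.3, between the reporting instructions and the causality subsection, was not available. It lies outside Section 13.5.

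Priority: nice to have.

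**What to change.** In Section 13.5, keep the ocular tabulation and the treatment-related summary as planned, and add for all enrolled subjects:

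1. a summary of all adverse events, split by ocular/non-ocular and by relatedness;
2. a table or listing of all serious adverse events, including deaths, with the same splits.

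It would help to state in the same place that the treatment-related summary includes non-ocular events, and that relatedness follows the definitions in the subsection numbered 12.3.1.

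The cost is one or two further tables or listings from forms the plan already requires. No new data, visits or subjects are needed. This is a free improvement.

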### **14. GCP, ICH and ETHICAL CONSIDERATIONS**

This study will be conducted in compliance with Good Clinical Practices (GCPs), including International Harmonization (ICH) Guidelines, and in general, consistent with the 1996 version of the Declaration of Helsinki. In addition, all applicable local, state and federal requirements will be adhered to.

This study is to be conducted in accordance with Institutional Review Board regulations. The investigator will obtain appropriate IRB/ethics committee approval prior to initiating the study.

The study will be registered with [clinicaltrials.gov](http://clinicaltrials.gov).

#### ***14.1 Confidentiality***

The data collected will be data typical for the procedure(s) when performed on eyes outside the study. Any data collected will become part of the patient's clinical record. The data will be subject to the same privacy and confidentiality as other data in the clinical record.

Only the principal investigator, research consultant and clinic staff will have access to the data collected. All data shared outside the practice will be de-identified; patients' protected health information will not be available and will not be reported in any analyses or publications. No data will be sold to third parties. De-identified data may be used for future research.

## 15. STANDARD EVALUATION PROCEDURES

**Table 15.1. Proposed Visits and Study Assessments**

(visits are by patient, with both eyes tested)

Activity	Pre-operative	Operative	Postoperative		
	Visit 1	Visit 2	Visit 3	Visit 4	Visit 5
			1 Day	1 Month	3 Months
Informed Consent	X				
Demographics	X				
General Information: Medical History	X				
Surgery		X			
Manifest refraction	X			X	X
Monocular uncorrected distance VA	X		X	X	X
Monocular corrected distance VA	X			X	X
Binocular uncorrected and best-corrected distance VA				X	X
Binocular uncorrected and best distance-corrected intermediate VA (80 cm)				X	X
Binocular uncorrected and best distance-corrected intermediate VA (66 cm)					X
Binocular Defocus Curve					X
Monitor for Adverse Events and Device Deficiencies		X	X	X	X
Complete Exit Form 					X

 Complete Exit Form upon termination of subject participation, or at Visit 5, whichever occurs first.

\* To be performed if deemed necessary by the investigator

## 16. CONFIDENTIALITY

No protected health information (PHI), including the patient's name and date of birth, will be collected; to ensure this, no PHI information is permitted to be entered on any of the Case Report Forms (CRFs). Subjects will only be identified by subject IDs and identities will be removed at the initial visit so that there is no further need to protect or destroy the information. Collected information will only be used for purposes of this study and no information will be sold to third parties. The non-PHI information collected may be used for future research, though there is currently no plan to do so.

## 17. FINANCIAL AND INSURANCE INFORMATION/STUDY RELATED INJURIES

Every effort to prevent study-related injury will be taken by the Study Doctor and staff. In the event a patient is injured as a direct result of the study while following the Study

Doctor's instructions and the study requirements, the patient will be instructed to contact his or her doctor immediately. The Study Doctor is to treat the injured subject as needed for those injuries caused directly by this research study. In the event of injury or illness caused by or occurring during a subject's participation in this research study, all charges for medical care provided to the subject will be billed to his or her insurance company. The Study Doctor or Sponsor does not offer to cover the medical care costs for injuries or illnesses that are not caused directly by the research study. The Sponsor does not offer to provide any other compensation, unless specifically agreed to elsewhere in this document. This information will be provided to each study subject before the start of the study in the consent form.

## **18. STUDY ENDPOINT CRITERIA**

### ***18.1. Patient Completion of Study***

If a study patient has completed the final visit (Visit 5) of the study, he/she is considered to have completed the study.

### ***18.2. Patient Discontinuation***

Each study patient may voluntarily discontinue the study at any time they choose. Study patients who cannot complete the study for administrative reasons (e.g., non-compliance, failure to meet visit schedule, etc.) will be discontinued from the study. Study patients discontinued during the enrollment phase (prior to surgery) of the study will be replaced.

### ***18.3. Patient Termination***

A study patient will be terminated if the study patient develops any severe adverse event that may be related to the study. A study patient will receive appropriate treatment at the discretion of the investigator. Notification of termination will be clearly documented. These study patients are considered to have completed the study and will not be replaced.

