### 9.2.2. Operative (Surgery)

All subjects will undergo cataract surgery with implantation of the Clareon IOL. The surgeon's usual standard of care with regard to treatment and medication will be used for all study subjects. Surgery planning and IOL power calculation will be performed using the surgeon's preferred method, with an initial a-constant provided by Alcon. The Barrett toric calculator will be used to estimate residual astigmatism.

Surgical findings will be recorded and any adverse events/serious adverse events (AEs/ SAEs) occurring during surgery will be noted at this visit. Any other problems during surgery and comments regarding surgery will be documented.

Any subject whose surgery is not completed successfully will be documented in the appropriate case report form. These subjects will be monitored for safety but clinical performance data may be excluded from the analysis.

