### 9.2.6. Exit Procedures

In the event of premature exit from the study, all study related examinations should be completed where possible. The Exit CRF should be completed, noting that the subject did not complete the study and the reason for premature study exit. If no premature exit from the study occurs, the Exit CRF should be completed at the end of Visit 5 (Postoperative 3 Months).

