#### ***9.4. Unscheduled Visits***

Unscheduled exams may be conducted at the discretion of the Investigator with all relevant information from the exam recorded in the source documents and on the Unscheduled Visit pages within the CRF booklet.

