### ***18.5. Study Completion***

The study will be complete when all enrolled patients have completed Visit 5 or have been terminated from the study.

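### Section 18.3 makes termination mandatory after a severe, possibly related adverse event, so unheld Visits 4 and 5 lapse: later ocular events may be under-counted and the 1-to-3-month refraction change is lost for subjects still labelled completers

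*Combined protocol and SAP*

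**What the plan says.** Section 18.3 makes termination automatic: "A study patient will be terminated if the study patient develops any severe adverse event that may be related to the study". Treatment is then at the investigator's discretion, and the section ends: "These study patients are considered to have completed the study and will not be replaced". It neither orders nor forbids further study visits.

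Two other places treat termination as the alternative to the last visit. Section 18.5: "The study will be complete when all enrolled patients have completed Visit 5 or have been terminated from the study". The footnote to Table 15.1: "Complete Exit Form upon termination of subject participation, or at Visit 5, whichever occurs first".

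On completion, 18.1 says: "If a study patient has completed the final visit (Visit 5) of the study, he/she is considered to have completed the study". For a premature exit, 9.2.6 has the Exit CRF completed "noting that the subject did not complete the study and the reason for premature study exit".

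Section 13.2 places adverse event inquiry at each visit. Section 13.5 tabulates ocular events by type, severity, duration and frequency. The primary outcome (8.1) is the change in spherical equivalent between Month 1 and Month 3. Section 10.2 gives its summaries for eyes that complete the study, and 10.2.1 tests within-treatment changes by TOST.

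**The concern.** By the time the rule usually applies, the lens is in the eye, so termination withdraws no exposure in that eye. What it withdraws is observation, and it does so in the subjects whose safety data matter most. Subjects with mild, moderate or unrelated events are asked about problems and examined again at Visits 4 and 5. A subject with a severe, possibly related event is not, if the event comes before those visits.

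Two results are exposed. The first is the frequency of later ocular events in 13.5, in the affected eye or its fellow. The second is the primary outcome, because without the Visit 5 refraction there is no 1-to-3-month change for either eye. The missing values would not be a random subset, since they arise from a severe event thought possibly related to the study. The completer label then makes it unclear whether these eyes belong in the 10.2 summaries.

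**Working it through.** The plan states no figure on this point, so the check is a reading of the sections against each other, followed by arithmetic for scale.

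**1. Does termination end the scheduled visits?** Section 18.3 does not say so outright. But 18.5 and the Table 15.1 footnote set termination against Visit 5 as either/or, and no section schedules a contact after termination. With inquiry attached to visits (13.2), scheduled inquiry lapses. Outside the schedule, 9.4 says: "Unscheduled exams may be conducted at the discretion of the Investigator". By contrast, 9.2.2 says of subjects whose surgery was not completed successfully: "These subjects will be monitored for safety but clinical performance data may be excluded from the analysis". Section 18.3 has no such line.

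**2. Scheduled observation lost.** Windows from Table 9.2-1, counted from surgery on the last eye: 1-day visit at 2 to 36 hours (0.08 to 1.5 days); Visit 4 at 30 ± 10 days (day 20 to 40); Visit 5 at 90 ± 20 days (day 70 to 110).

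- Terminated at the 1-day visit: 70 − 1.5 = 68.5 to 110 − 0.08 = 109.9 days, nominally 90 − 1 = 89. Visits 4 and 5 are lost.
- Terminated at Visit 4: 70 − 40 = 30 to 110 − 20 = 90 days, nominally 90 − 30 = 60. Visit 5 is lost.
- Terminated at Visit 5: nothing is lost.

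In the first two cases the 1-to-3-month refraction change cannot be computed.

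**3. Number of subjects.** The documents give no rate, so p is assumed. Expected count = 30p; chance of at least one = 1 − (1 − p)^30.

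- p = 1%: 30 × 0.01 = 0.3; 1 − 0.99^30 = 0.26
- p = 3%: 30 × 0.03 = 0.9; 1 − 0.97^30 = 0.60
- p = 5%: 30 × 0.05 = 1.5; 1 − 0.95^30 = 0.79

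Section 11 asks for at least 23 subjects and enrols 30, a margin of 30 − 23 = 7. A loss of one or two stays well inside it.

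**4. What the completer label can do to the primary percentage.** Suppose, for illustration, that 48 eyes are stable and one subject (two eyes) was terminated before Visit 5. Counting that subject's eyes in the denominator gives 48/60 = 80.0%, the hypothesised figure. Leaving them out gives 48/58 = 82.8%. Section 10.2 does not spell out which applies to a completer with no 3-month value.

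**The case against.** The best defence is that safety follow-up does not stop. A reader might infer from 18.3 that it does, or that the duration of the triggering event is lost. The documents do not support either reading. Section 13.4 makes the investigator responsible for follow-up after the study and requires the resulting data to be documented and available to the coordinator. Section 13.3 requires outcome, and a resolution date if the event has resolved. Section 9.2.6 asks for all study examinations at premature exit where possible, and 9.5 asks for an assessment of anyone who discontinues before Visit 5. Section 10.1 keeps every enrolled subject in the safety evaluation. Most of the duration worry is thereby answered. What remains is that no contact is scheduled, that the coordinator and Medical Monitor decide when later data go on the CRF, and that the completer label leaves it unclear whether the premature-exit provisions apply. An exit examination is also a single occasion and cannot detect a later event.

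A reader might also infer that a procedure-related event goes unassessed, because the causality section (numbered 12.3.1) rates relationship to the device. That does not hold: 13.3 also requires relationship to the study treatment. Moreover, an event that is severe by intensity may often be serious as well, which brings it under the reporting updates in 13.3.

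On completion, 18.1 does not say that Visit 5 is the only route, so 18.3 can be read as adding a second. That is fair as literal reading, and this is tension in wording more than flat contradiction. It still matters, because the 10.2 summaries and lens reimbursement in 9.1 both turn on who completed.

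Finally, it is tempting to say that only descriptive safety tables are touched. That is too generous to the plan: a subject terminated before Visit 5 contributes no change to the primary outcome or to TOST. One limit applies. Section 10.1 already restricts efficacy to eyes with uncomplicated surgery, so for an intraoperative complication the affected eye may be out anyway, and the loss then falls on the fellow eye.

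**Conclusion.** The point holds and is minor. As written, 18.3 removes scheduled inquiry and refraction from subjects with a severe, possibly related event that occurs before Visit 5, and still counts them as completers. Later ocular events in either eye may be under-counted, and the primary change is missing for those subjects. The scheduled observation lost is nominally 60 days if termination comes at Visit 4 and 89 days if it comes at the last eye's 1-day visit.

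At the assumed 1% to 5% of subjects, about 0.3 to 1.5 of 30 are affected, with a 26% to 79% chance of at least one. That range is an assumption; only the windows and the 30 subjects come from the documents. The conclusion also rests on reading termination as the end of scheduled visits, which 18.5 and Table 15.1 support but 18.3 does not state. It does not extend to the record of the triggering event, which other sections largely secure.

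**What to change.** Replace the first sentence of 18.3 with:

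> A subject who has received a study lens and has a severe adverse event that may be related to the study remains on the scheduled Visit 4 and Visit 5 assessments (adverse event inquiry, manifest refraction and visual acuity), unless the subject declines or the investigator judges that continued participation poses a risk to health (9.5). If only one eye has been operated on, the windows count from that eye.

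Replace its last sentence with:

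> These subjects will not be replaced and are considered to have completed the study only if they complete Visit 5 (18.1).

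Add to 9.1:

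> A subject who exits early because of such an event is still reimbursed for the lenses.

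The 9.1 sentence is needed because reimbursement there depends on completing the study, and the narrower completer wording would otherwise take it from subjects who exit early. Treatment stays at the investigator's discretion, and 9.5 still allows discontinuation for health risk.

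The cost is wording in two sections and at most two already planned visits for a few subjects. Some of them may decline, so some values will still be missing.
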